7.4.2. Calculation of the Primary Endpoint

Criteria for Meeting the Primary Endpoint

Subjects must:

1. Receive an Imaging Dose
2. Receive at least one Therapeutic Dose
3. Have a reduction of each pre-therapeutic dosing (baseline) antihypertensive medication $\geq 50\%$ for a minimum of six consecutive months beginning during the 12-Month Efficacy Phase of the study, during which no new, long-term antihypertensive medication is introduced and maintained for longer than 14 days.

Considerations

1. The introduction of a new, transient (i.e., duration ≤ 14 days) antihypertensive medication regimen at any point during the study will not disqualify a subject from being able to achieve the primary efficacy endpoint. Short duration therapy may be instituted to address an acute increase in blood pressure that might be associated with a transient increase in catecholamine release secondary to a variety of factors including tumor cell death. On the contrary, the primary outcome measures chronic control of hypertension necessitated by long term catecholamine secretion by the active tumor.
2. A transient (i.e., duration ≤ 14 days) dose increase over the baseline dose of an existing antihypertensive medication regimen at any point during the study will not disqualify a subject from being able to achieve the primary endpoint. Existing antihypertensive therapy may be increased for a short duration to address an acute increase in blood pressure that might be

associated with a transient increase in catecholamine secretion secondary to a variety of factors including tumor cell death.

3. The introduction of a new, long-term (i.e., duration > 14 days) antihypertensive medication regimen after receiving a therapeutic dose will disqualify a subject from being able to achieve the primary endpoint while the subject is still taking any dose of the new medication. If the new long-term antihypertensive medication is discontinued, the start date for assessment of the primary endpoint is the date when both the new medication is discontinued and the baseline antihypertensive medications are reduced $\geq 50\%$.
4. New long-term antihypertensive medications introduced before Therapeutic Dose #1 is administered are considered part of the baseline antihypertensive medication regimen that must be reduced by at least 50% for achieving primary endpoint.
5. A long-term (i.e., duration > 14 days) increase in dose over the baseline dose of an existing antihypertensive medication regimen after receiving a therapeutic dose will not disqualify a subject from being able to achieve the primary endpoint if all antihypertensive medications are reduced to a level of 50% or below the baseline dose for at least six consecutive months in duration, since the increase may have been made before a tumor response was obtained. The introduction of a new antihypertensive medication with a duration of >14 days will be considered as the end of a benefit duration period. The start date for the duration of response is the date that the last antihypertensive medication is reduced to the level of 50% or below the baseline dose.
6. The introduction of an antihypertensive medication regimen or increase in existing antihypertensive medication regimen that occurs after the subject has already met the primary endpoint (i.e., had a $\geq 50\%$ reduction of all antihypertensive medications for at least six consecutive months) will not disqualify the subject from achieving the primary endpoint.

Calculation of Duration of Response

The six-month duration of the primary endpoint response begins on the date during the 12-Month Efficacy Phase when all baseline antihypertensive medications have been reduced by at least 50% and any new medications are discontinued (the date post-therapeutic dosing when the reduction of the last antihypertensive medication reduced by at least 50% or the new medication is discontinued) and ends once six consecutive months (i.e., 168 days) duration of sustained $\geq 50\%$ reduction has been achieved, regardless of the phase of the study during which the end date of the response occurs (i.e., 12-Month Efficacy Phase vs. Long-Term Follow-Up Phase).

The end date for which the duration of the $\geq 50\%$ reduction of all antihypertensive medications is determined as the earlier of:

- a. the date that the subject no longer meets the criteria of having a $\geq 50\%$ reduction of all baseline antihypertensive medications (i.e., the starting date of a new long-term continuing antihypertensive medication or a dose change in an existing regimen of antihypertensive medication that exceeds the $\geq 50\%$ reduction of the baseline dose that is greater than 14 days in duration and continues without a reduction to the $\geq 50\%$ level)

OR

- b. the date of the subject's last applicable recorded study-related disposition date. If the subject has discontinued the study prior to the end of the 12-Month Efficacy Phase due to any of the following reasons:
- Withdrew consent
 - Was lost to follow-up
 - Death
 - Withdrew due to progressive disease
 - Received other anticancer therapy
 - Experienced an adverse event resulting in study discontinuation

The last participation date is the corresponding disposition date within the 12-Month Efficacy Phase (i.e., date that the subject withdrew consent, was lost to follow-up, died, withdrew due to disease progression, received other anticancer therapy, or experienced an adverse event resulting in study discontinuation).

If the subject has completed the 12-Month Efficacy Phase but continues to meet the criteria of having a $\geq 50\%$ reduction of all antihypertensive medications, the last applicable disposition date would be the long-term follow-up completion/discontinuation date.

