7.4.1. Primary Analysis: Reduction in Use of Antihypertensive Medication

The primary endpoint for this trial is the proportion of study subjects with a reduction (including discontinuation) of all antihypertensive medication by at least 50% for at least six months or two cycles of iobenguane I 131. The 50% reduction is determined separately for each baseline medication, based on the total daily dose of the antihypertensive medication(s) on the day of the first therapeutic dose.

A benefit duration period is measured by maximum duration as follows. The benefit duration period commences when the subject's medication is reduced to a level below 50% of baseline, and continues until the subject's medication rises above 50% of baseline, until the onset of a new antihypertensive medication of >14 days' duration, or to the last subject date as described in section 7.4.2, Primary Endpoint Calculation. A benefit duration period must begin during the 12-Month Efficacy Phase but may end during the Long-term Follow-up Phase. If the subject discontinues participation in the study before the Month 12 efficacy evaluation, the last date for calculation of the duration of benefit is the date of termination in the study.

For purposes of illustration, the following examples are provided (Month refers to the number of 28-day months after the first Therapeutic Dose).

- Example 1: A subject experiences the clinical benefit from the beginning of Month 2 to the beginning of Month 4, and then again from the beginning of Month 5 to the beginning of Month 12. Since the maximum duration of the benefit was 7 months, the subject is considered a success on the primary endpoint.
- Example 2: A subject experiences the clinical benefit from the beginning of Month 2 to the beginning of Month 4, and then again from the beginning of Month 6 to the beginning of

Month 11. Even though the subject experienced the clinical benefit for a total of 7 months, the maximum duration of the benefit was only 5 months, so the subject is considered a failure on the primary endpoint.

- Example 3: A subject experiences the benefit from the beginning of Month 2 to the beginning of Month 9. At Month 10, the subject receives another anticancer treatment and is discontinued from the study. Since the maximum duration of the benefit was 7 months, prior to discontinuation, the subject is considered a success on the primary endpoint.

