7.9. Sensitivity Analysis

A sensitivity analysis will be performed on the primary endpoint where at least six months of the duration of clinical benefit is required to be completed within the 12-month efficacy period. An additional sensitivity analysis will treat subjects who begin a new antihypertensive medication following therapeutic dosing that continues for at least 14 days as non-responders.

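### For new antihypertensives, the primary endpoint limits the length of one rescue course but never joins or totals courses, so repeated short courses can be scored as six months of benefit

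*SAP*

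**What the plan says.** SAP 7.4.2 requires each baseline antihypertensive to be reduced by at least half for six consecutive months (168 days), starting within the 12-month efficacy phase. Criterion 3 describes this as a period "during which no new, long-term antihypertensive medication is introduced and maintained for longer than 14 days".

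Consideration 1 allows short rescue with a new drug. It defines transient as 14 days or less and says that such an "antihypertensive medication regimen at any point during the study will not disqualify a subject from being able to achieve the primary efficacy endpoint". The reason given is an acute, passing catecholamine rise, for example from tumor cell death, whereas "the primary outcome measures chronic control of hypertension necessitated by long term catecholamine secretion by the active tumor". Consideration 2 gives the same allowance for a temporary increase over the baseline dose of an existing drug: such a change to an existing "antihypertensive medication regimen at any point during the study will not disqualify a subject from being able to achieve the primary endpoint". Consideration 3 blocks response only while a new regimen of more than 14 days is being taken.

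The rules that end a benefit period are:

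- **New drug, 7.4.1:** the period runs "until the onset of a new antihypertensive medication of >14 days' duration".
- **New drug, 7.4.2 end rule (a):** it ends at the start of a new long-term, continuing drug.
- **Existing drug, 7.4.1:** the period "continues until the subject's medication rises above 50% of baseline", with no 14-day exception.
- **Existing drug, 7.4.2 end rule (a):** it ends only if the rise is greater than 14 "days in duration and continues without a reduction to the" halved level.

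The second sensitivity analysis in SAP 7.9 treats subjects who "begin a new antihypertensive medication following therapeutic dosing that continues for at least 14 days as non-responders". Protocol 13.3.2.1 contains no 14-day allowance.

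**The concern.** The allowance is justified as covering an acute event. A need for added blood-pressure treatment that keeps returning over six months is not acute, yet the written rules can score it as unbroken benefit. That is the opposite of the chronic control the SAP says it measures.

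The gap can only add responders. The trial is open label and single arm, and medication changes are a matter of physicians' judgment (Protocol 11.4 and 11.5.12), so course length is not insulated from knowledge of treatment. The primary conclusion rests on one responder count compared with a fixed 10% limit.

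**Working it through.** **1. The plan's own sample size.** Inputs from SAP section 6: p0 = 0.10, p1 = 0.25, one-sided alpha 0.025, power 0.90.

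n = [(1.960 × √(0.10 × 0.90) + 1.282 × √(0.25 × 0.75)) / 0.15]² = [(0.588 + 0.555) / 0.15]² = 58.06

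This agrees with the stated 58. It confirms the design rates used in step 4 and is not affected by this point.

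**2. What ends the period for a new drug.** Criterion 3, Consideration 3, 7.4.1 and end rule (a) all turn on one regimen lasting more than 14 days. The start rule in 7.4.2 requires new drugs to be off on the date the period begins and says nothing about later short courses. Neither document sets a minimum gap, a maximum number of courses, a day total, or a definition of when two courses form one regimen.

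**3. Rescue days that fit inside 168 days.** The patterns are illustrative assumptions, because the documents give no rescue frequency. They apply to a new drug, with each course read as a separate regimen.

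| Pattern | Rescue days | Share of 168 | Primary analysis | 7.9 analysis |
|---|---|---|---|---|
| 13 on, 1 off | 12 × 13 = 156 | 93% | responder | responder |
| 14 on, 7 off | 8 × 14 = 112 | 67% | responder | non-responder |
| 14 on, 14 off | 6 × 14 = 84 | 50% | responder | non-responder |

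A course of exactly 14 days is allowed in the primary analysis (the limit there is more than 14) but fails in 7.9 (at least 14). What 7.9 leaves open is therefore repeated courses of 13 days or less. It also does not cover dose increases of existing drugs.

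**4. How close the success limit is.** SAP 7.4.1 requires the Agresti-Coull 95% lower bound in the Full Analysis Set to exceed 0.10. With ñ = n + 1.96² and p̃ = (x + 1.96²/2)/ñ, the lower bound is p̃ − 1.96 × √(p̃(1 − p̃)/ñ). The size of the Full Analysis Set is not stated, so 58 and 75 (planned evaluable and planned enrolled) are taken as a range.

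- n = 58, x = 11: ñ = 61.84, p̃ = 0.2089, bound = 0.2089 − 0.1013 = 0.1076, success. With x = 10 the bound is 0.0944, failure.
- n = 75, x = 13: ñ = 78.84, p̃ = 0.1893, bound = 0.1893 − 0.0865 = 0.1028, success. With x = 12 the bound is 0.0924, failure.

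At the planned 25%, the expected counts are 0.25 × 58 = 14.5 and 0.25 × 75 = 18.75, or about 14 and 19. Falling from these to failure takes 14 − 10 = 4 or 19 − 12 = 7 responders.

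**5. Existing drugs.** 7.4.1 ends the period at any rise above half of baseline. Consideration 2 and end rule (a) tolerate a rise of up to 14 days. Whether repeated short increases can be scored as benefit depends on which passage governs. This is a conflict to be settled, separate from the gap in step 2.

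**The case against.** The strongest reply is that reading the allowance course by course is an interpretation. The SAP speaks of a regimen and contrasts transient with long-term. A programmer could treat 13 days on, 1 off, 13 on of the same drug as one long-term regimen, which would suit the stated purpose. This stands as far as it goes: the gap arises from silence, and a reader who concludes that the SAP expressly permits any number of short courses goes further than the text. But the silence means that two programmers could score the same subject differently on the primary endpoint.

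The wording of Considerations 1 and 2 could also mean only that a subject remains able to qualify later. Consideration 5 uses similar wording for long increases that must still be followed by six consecutive qualifying months. For new drugs this does not help, because the end rules themselves act only beyond 14 days. For existing drugs it has force, given 7.4.1.

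The 7.9 analysis already scores new-drug courses of 14 days or more as non-response, so patterns built on 14-day courses would be exposed there. That is correct, and the remaining gap is narrower than the primary rules alone suggest.

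Finally, SAP 7.4.1 plans a response listing with medication dates and doses, and by-subject figures of medication and blood pressure, so repeated rescue would be visible. It would, but neither output changes responder status.

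**Conclusion.** The point holds for new antihypertensives. Read literally, SAP 7.4.1 and 7.4.2 let repeated short courses be scored as a full six-month response, and 7.9 does not catch courses of 13 days or less. In the extreme illustrative pattern, rescue covers 156 of 168 days (93%). For existing drugs, the finding is that passages conflict and that 7.9 has no analysis of dose increases.

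A reader might infer that this gap would reverse the trial's conclusion. The documents do not support that. The 4 to 7 responders are simply the distance between the expected count and the success limit, and would be the same for any criticism of the endpoint. Nothing indicates how many subjects, if any, had repeated rescue, and each would also have had to keep every baseline drug at least halved for 168 days. What can be said is that the effect is unknown, its direction is toward success, and the margin is a few responders. This rests on a Full Analysis Set of 58 to 75 and a true rate of 25%.

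**What to change.** 1. **SAP 7.9 (the main change).** Add a sensitivity analysis of the primary endpoint in which the benefit period ends once cumulative days on any new or above-baseline antihypertensive, counted from the start of that period, exceed a pre-specified total. One choice is 14 days, with 28 as an alternative because two therapeutic doses are given and each could be followed by a transient episode. List cumulative rescue days for each responder.
2. **SAP 7.4.2.** State that repeat courses of the same new drug separated by less than a pre-specified gap are scored as one regimen when testing for more than 14 days. This is not sufficient alone: joining only gaps shorter than 14 days would leave a 14-on, 14-off subject (84 of 168 days) a responder. That is why the cumulative analysis carries the main weight.
3. **SAP 7.4.1 and 7.4.2.** For temporary increases of existing drugs, reconcile the 7.4.1 end rule with Consideration 2 and end rule (a).

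These are scoring rules and change no subject's treatment. The cost is SAP wording and modest programming, because Protocol 11.5.3 already requires medications and changes in total daily dose to be recorded, and the SAP 7.4.1 listing already uses dates of use and doses. The downside is that the response rate may fall slightly. The gap and the total are conventions and should be fixed before database lock.

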Use of antihypertensive medication will be measured through standard, ongoing reporting of concomitant medications throughout the study until completion of the follow-up period. Tumors will be measured by computed tomography (CT) with contrast or magnetic resonance (MR) imaging at baseline and at 3, 6, 9 and 12 months after the first Therapeutic Dose. Obtaining renal volume for each kidney is required at baseline. A bone scan will be performed at Screening/baseline and if probable metastatic disease is observed or suspected, additional bone scans will be performed at Month 3, 6, 9, 12. Overall tumor response at 3, 6, 9 and 12 months per RECIST criteria will be assessed centrally by independent, blinded readers. FDG scans may also be performed at baseline and 3, 6, 9, and 12 months to assess viable tumor tissue. Tumor markers [serum chromogranin A, plasma free metanephrines and normetanephrines, 24 hour urinary vanillylmandelic acid (VMA), plasma catecholamines (dopamine, epinephrine and norepinephrine), 24 hour urinary catecholamines (dopamine, epinephrine and norepinephrine) and urinary metanephrines and normetanephrines] will be evaluated by a central laboratory. Testing for tumor markers will occur at baseline, every two weeks for the first 24 weeks after the first Therapeutic Dose starting at Week 2, and monthly during months 7-12. Renal function will be assessed through either creatinine clearance or Glomerular Filtration Rate (GFR) at baseline and at the Months 6 and 12 Efficacy Visits. Evaluation of thyroid function (T3, T4 and TSH) and clinical evaluation of possible dry mouth will be performed at the 12 month Efficacy Visit. Use and dose of antihypertensive, pain and other medication required for tumor associated signs and symptoms will be recorded on an on-going basis throughout the study until completion of the follow-up period. Subject-reported Quality of Life measurements will be obtained through the EORTC QLQ-C30 v3 and the NIH Quality of Life and Symptoms Questionnaire for Pheochromocytoma and Paraganglioma. The frequency of the procedures is summarized in the Schedule of Procedures (Appendix VII). Subject may undergo additional assessments as warranted (for example, to confirm tumor response) at unscheduled visits.

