Safety will be assessed through analyses of treatment emergent adverse events (AEs), as well as baseline and pre- and post-infusion ECGs, physical examinations, vital signs measurements, laboratory measurements (including clinical chemistry, hematology and urinalysis), and human radiation absorbed dose estimates to target lesions and normal organs. Subjects will be monitored for serious and non-serious AEs, and Adverse Events of Special Interest see Section 12.

After the 12 month assessment, subjects enter long-term follow-up and remain in follow-up for 5 years following the first therapeutic dose. Subjects will be followed for overall survival for 5 years following the first therapeutic dose. In years 2-5 post-treatment (or until a patient experiences disease progression, start of another anticancer therapy or death), data on tumor response, tumor markers and clinical benefit (including use of antihypertensive medication) will be collected through assessments provided as institutional standard of care. If standard of care is not providing such assessments, they will be offered by the study site.

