11.5.17 Long-Term Follow-Up

Subjects will be followed for Events of Special Interest (Appendix VI), which includes post radiation toxicity as outlined in Section 12. Thereafter, subjects enter long term follow up and remain in follow up for 5 years after the first Therapeutic Dose of Ultratrace iobenguane I 131. During this period, subjects will be followed for adverse events of special interest and overall survival and concomitant medication usage. In years 2-5 post-treatment (or until a subject experiences disease progression, start of another anticancer therapy or death), data on tumor response, tumor markers and clinical benefit (including use of antihypertensive medication) will be collected through assessments provided as institutional standard of care. If standard of care is not providing such assessments, they will be offered by the study site.

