Safety will be assessed through analyses of treatment emergent adverse events (TEAEs), as well as baseline and pre- and post-infusion ECGs, physical examinations, vital signs measurements, and laboratory measurements (including clinical chemistry, hematology and urinalysis). Serious adverse events (SAEs) and non-SAEs will be collected and reported until 16 weeks following the last administration of iobenguane I 131. Adverse events of special interest (AESIs), including radiation toxicity, reported beyond 16 weeks after the last therapeutic dose of study drug will be collected during the 12 month assessment period and until completion of the follow up period.

After the 12-month assessment, subjects enter long-term follow-up and remain in follow-up for a total of 5 years following the first therapeutic dose. Subjects will be followed for AESIs and overall survival for 5 years post-treatment. In years 2-5 post-treatment (or until a subject experiences disease progression, start of another anticancer therapy or death), data on tumor response, tumor markers and clinical benefit (to month 18 only) will be collected through assessments provided by institutional standard of care.

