7.4.4. Other Analyses of Reduction in Use of Antihypertensive Medications

Other analyses of use of antihypertensive medications will include descriptions of the maximum duration of benefit (reduction by at least 50%) beginning during the 12-Month Efficacy Phase, and the proportion of subjects discontinuing all antihypertensive medications completely for at least 6 months beginning during the 12-Month Efficacy Phase. Additional correlations between relative changes in antihypertensive medications and other endpoints may be performed as exploratory analyses. The Spearman correlation coefficient will be reported for any exploratory analyses.

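### For Month 12 completers the end-of-benefit date can lie beyond the benefit data the SAP says are collected, so the maximum-duration outputs may include unobserved time

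*SAP*

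**What the plan says.** SAP section 7.4.2 ends a benefit period at the earlier of two dates. Date (a) is the loss of the 50% reduction or the start of a new long-term antihypertensive. Date (b) is the last applicable disposition date. For subjects who leave before Month 12, (b) is the date of the event that took them off study, and progression, other anticancer therapy and death are on the list. For subjects who complete Month 12 and are still reduced, "the last applicable disposition date would be the long-term follow-up completion/discontinuation date". SAP section 7.4.1 requires the benefit to begin in the efficacy phase but lets it end in long-term follow-up.

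SAP section 4.1 keeps subjects in follow-up for five years from the first therapeutic dose. It says that "tumor markers and clinical benefit (to month 18 only) will be collected through assessments provided by institutional standard of care", and it limits years 2-5 to the time "or until a subject experiences disease progression, start of another anticancer therapy or death".

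The protocol says two things. Section 9.1 contains a similar stopping clause, "In years 2-5 post-treatment (or until a patient experiences disease progression, start of another anticancer therapy or death), data on", followed by a list that includes clinical benefit and, expressly, antihypertensive use. It has no Month 18 limit. The same section also states: "Use of antihypertensive medication will be measured through standard, ongoing reporting of concomitant medications throughout the study until completion of the follow-up period". Section 11.5.17 says of long-term follow-up that "subjects will be followed for adverse events of special interest and overall survival and concomitant medication usage".

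The full length of benefit is used in SAP section 7.4.4, which plans "descriptions of the maximum duration of benefit (reduction by at least 50%) beginning during the 12-Month Efficacy Phase", and in Tables 14.2.1.2A and 14.2.1.2B and Figure 2.

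**The concern.** End date (a) can be seen only while antihypertensive use is being recorded. Once recording stops, (a) cannot occur in the data and (b) decides by default. If (b) is then a survival follow-up date years later, the interval between the last medication record and that date is counted as benefit. That amounts to carrying the last state forward, which sits badly with the statement in SAP section 7.6 that nothing is imputed in the primary analysis.

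Two outputs are at stake. The first is the maximum-duration summaries, which could report time that nobody observed. The second, under a further condition, is responder status for late onsets: a benefit interrupted by a new anticancer therapy would be cut at that date before Month 12, but perhaps not after it.

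**Working it through.** **Inputs**
- Required duration: 168 days (SAP 7.4.2). With the 28-day month of SAP section 7, 6 × 28 = 168, so the SAP's figure reproduces.
- Latest permitted onset: the end of 12 calendar months (SAP section 7), taken as Day 365.
- Month 18: the window is Day 518 to Day 578 (SAP Appendix 1), midpoint (518 + 578)/2 = Day 548. That window is given for tumour response and tumour markers. Applying it to clinical benefit is an assumption.
- End of follow-up: five years, 5 × 365.25 = 1826.25, taken as Day 1826.

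**1. Maximum duration, if SAP 4.1 governs.** The longest stretch that can be counted without benefit data is 1826 − 548 = 1,278 days. In calendar months this is 1,278/30.44 = 42.0. As a share of the credited interval:
- Onset Day 90: 1,278/(1826 − 90) = 1,278/1,736 = 74%.
- Onset Day 365: 1,278/(1826 − 365) = 1,278/1,461 = 87%.

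These are upper limits. They need a subject who stays in follow-up to Year 5 and has no medication record after Month 18.

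**2. Does the Month 18 stop reach the six-month endpoint?** The latest onset completes on 365 + 168 = Day 533.

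| Reading of Month 18 | Latest onset with 168 days observed | Shortfall for onset on Day 365 |
|---|---|---|
| Day 504 (18 × 28) | 504 − 168 = Day 336 | 533 − 504 = 29 days |
| Day 518 (early edge of window) | 518 − 168 = Day 350 | 533 − 518 = 15 days |
| Day 548 (midpoint) | 548 − 168 = Day 380 | none |
| Day 578 (late edge of window) | 578 − 168 = Day 410 | none |

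At the midpoint every permitted onset is fully observed. Only the two stricter readings leave a gap, and only for onsets in the last 29 or 15 days of the efficacy phase.

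**3. Does the stop at progression or new therapy reach it?** Onsets after 365 − 168 = Day 197 need data from beyond Month 12. Take onset on Day 300 and a new anticancer therapy on Day 400, which is 100 days. If (b) is the therapy date, the subject fails. If (b) may be a later follow-up date, the subject passes once that date reaches 300 + 168 = Day 468. The same 100 days placed from Day 200 to Day 300 fail outright, because the therapy then falls in the efficacy phase.

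**4. How many such subjects would matter?** SAP section 7.4.1 declares success when the Agresti-Coull lower limit exceeds 0.10. The limit uses z² = 3.84 and an adjusted size of 58 + 3.84 = 61.84, assuming 58 subjects in the analysis.
- 11 responders: (11 + 1.92)/61.84 = 0.209, lower limit 0.108, a success.
- 10 responders: (10 + 1.92)/61.84 = 0.193, lower limit 0.094, not a success.

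So one reclassified subject could decide a result at the threshold. The documents give no way to estimate how many subjects would follow the pattern in step 3.

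**The case against.** A reader might infer that benefit data do stop at Month 18, so that unobserved time is certain to be counted. The documents do not support that. The Month 18 limit appears only in a parenthesis in the SAP's overview. Protocol sections 9.1 and 11.5.17 and the Appendix VII schedule have antihypertensive or concomitant medication recorded through follow-up. If the protocol governs and recording is complete, end date (a) can be observed up to the date used in (b), and little or no time is unobserved. End date (a) also continues to apply after Month 12, so the follow-up date is not the only way a benefit period can end. This part of the objection stands: the demonstrated fault is a conflict over data collection that the end-date rule does not allow for.

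A reader might also infer that the rule inflates the primary endpoint. Step 2 rules that out for the Month 18 stop taken as Day 548. For progression or new therapy, Protocol section 9.7 makes both discontinuation criteria without a time limit. Example 2 in Protocol section 13.3.2.1 has a patient discontinued on starting another anticancer treatment at Month 15. On that reading the follow-up discontinuation date is the therapy date, and the Day 300 case ends at 100 days.

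That reading is plausible but not secured. SAP 7.4.2 attaches those reasons only to discontinuation before Month 12, and the SAP's version of Example 2 omits the Month 15 discontinuation. Protocol section 9.8 shows that a subject discontinued in the efficacy phase can remain in follow-up for survival, so the two endings need not coincide. It treats discontinuation during follow-up as a separate event, after which only events of special interest are followed.

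Finally, the duration outputs are descriptive and carry no success criterion. SAP section 7.9 already plans a sensitivity analysis that requires the six months to be completed within the efficacy phase. It covers responder status, but neither the primary analysis itself nor the duration outputs.

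**Conclusion.** The point holds in a limited form. Read with SAP 4.1, the end-date rule in SAP 7.4.2 can count time without benefit data in the maximum-duration outputs. The size is at most about 1,278 days, or 42 months, per subject. That assumes that SAP 4.1 governs, that Month 18 is Day 548, and that the subject is followed to Year 5 without a later medication record. If the protocol's recording to the end of follow-up is what happens, the excess shrinks towards zero.

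The Month 18 stop by itself leaves six-month responder status unchanged on the same assumption. Responder status for onsets after about Day 197 could be affected only if the long-term follow-up discontinuation date may fall after progression or a new anticancer therapy. The SAP does not define that date, so this is an open ambiguity and not a demonstrated bias. The sample size is not affected.

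**What to change.** 1. Reconcile SAP section 4.1 with Protocol sections 9.1 and 11.5.17, and state until when antihypertensive use is recorded, including after progression or a new anticancer therapy.
2. In SAP 7.4.2(b), for Month 12 completers still in benefit, set the end date to the earliest of: the last recorded antihypertensive medication review, progression, start of another anticancer therapy, death, or long-term follow-up completion or discontinuation. Do not add a fixed Month 18 cap, which could discard medication data that the protocol collects.
3. Treat subjects still reduced at their last medication record as censored there, and summarise duration in Tables 14.2.1.2A and 14.2.1.2B by Kaplan-Meier, the method that SAP section 7 already gives for time-to-event data. Mark censored subjects in Figure 2.

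The cost is SAP wording and minor programming, with no new data collection. Reported durations will be somewhat shorter.
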